# STUDY PROCEDURES/REGIMEN

#### STUDY FLOWCHART

This is a two-stage development and feasibility study to develop a complex intervention.

Page 23 of 50

ENGAGEMENT	DEVELOPMENT – 6 months
Regular Study Steering Group, and Study	A. Foundations – update literature review and evidence-base, write study documentation and apply for research ethics committee approval.
Management Group meetings	B. Co-production - components of the intervention through a series of scoping interviews with a minimum of 8 key stakeholders (representatives from organisations that offer DA and SP services), followed by 2 lay focus groups and then 3 co-production
Regular Public and Patient involvement & Engagement meetings On-going collation of mailing list of interested parties, with regular distribution of	workshops with 8 lay people and 4 pharmacy staff representatives in each workshop (total of 36 participants).
	C. Modelling – finalisation of the above intervention elements, with consideration of RE_AIM (Reach, Effectiveness, Adoption, Implementation, Maintenance)  plus ethics, data monitoring and finalisation of outcomes for feasibility study.
	FEASIBILITY – 18 months
	D. Recruitment and Training - Recruit 8 x pharmacies for intervention and 2 x pharmacies as comparisons, purposive sampling to cover rural/urban, small pharmacy/commercial store and differing socio-economic areas. Recruit and train a minimum of 3 members of staff from each pharmacy in intervention (total 24 staff).
updates Project website	E. Implementation of Intervention - Promotion of the service to the public, Implement intervention in the 8 pharmacies, data collection over 6 months in 8 x intervention pharmacies and 4 x comparison (control) pharmacies.
	F. Evaluation for acceptability - Using the Theoretical Framework for Acceptability of Healthcare Interventions.  These will be investigated with pharmacy staff in 3 x focus groups with 8 staff in each (total 24 participants), followed by interviews with 2 to 3 regular customers per intervention pharmacy (not people who have use the intervention) (total 16-24 participants). An e-survey will then be designed from the qualitative analysis themes, and distributed widely to members of the public, electronically using social media, with the aim of having 600 completed surveys.
	G. Feasibility of the intervention - Summary workshop with the 24 staff members, plus PPIE panel and Study Management Group to explore the feasibility of the intervention as a possible service and description of the intervention.
	H. Feasibility of a future cluster randomised controlled trial – Analysis and evaluation by the research to team to scope the requirements of a future cluster randomised controlled trial possible.
	DISSEMINATION – throughout study, and towards end of study
	Report qualitative findings using COREQ template  , and the details of the intervention using TIDieR  . Active dissemination via presentations and meetings with all partner and stakeholder organisations, and via mailing list and social media. Research publications: (i) reporting development and co-design; (ii) report of service use; (iii) report of focus group evaluation data.

# Schematic overview

# Methods - development phase

# A. Foundations

The literature review will be updated. Research Ethics Committee (REC) approval will be sought from the NHS Research Ethics Service (RES).

# **B. Co-development**

# 1. One-to-one scoping interviews with key stakeholders

A minimum of 8 scoping interviews will be held with representatives of relevant referral organisations (for example – Women's Aid, Samaritans, Emergency Department, Mental Health Crisis Team, Adult Social Care Domestic Abuse Co-ordinator, the Police, Addaction (now known as "We are with you")). They will be recruited via targeted e-mails followed up with a participant information sheet and consent form. In-depth semi-structured interviews will be conducted, using scenarios to map and ascertain appropriate referral and support pathways for different levels of severity and urgency for suicidal ideation or domestic abuse (and any accompanying alcohol or substance misuse), and appropriate content of an education and training resource for pharmacy staff delivering the intervention. Views will also be sought on requirements for appropriate mentoring of pharmacy staff in case of distress during the study, on the requirements for clinical record keeping and on the content of the client self-report evaluation questionnaire (to be used in the evaluation). Interviews will be recorded and transcribed. Data will be analysed using framework analysis. Recruitment and interviewing will continue until consensus and data saturation are achieved. These interviews will contribute to the development of the triage and referral tool. This will be an iterative process to create and embed appropriate referral pathways.

# 2. Lay focus groups

Alongside these interviews, two lay focus groups will be held: one for lay people with experience of domestic abuse, and one for lay people with experience of suicidal ideation. These groups will explore the lived experience and barriers to access for each issue, and will start the co-production process of the intervention. Representatives from each group will be invited to carry forward with the project, in to the co-production workshops. Each of the two groups will have 8 participants.

Members of the public will be recruited from relevant patient forums, relevant charities, survivor support groups, the local Recovery College etc. via distribution of a flyer (and social media post), or through contacts at those organisations. Expressions of interest will be followed up with a participation information sheet, consent form and a phone call from the researcher. Inclusion criteria are adults over 18 years of age, capable of informed consent, and an interest in supporting others suffering from suicidal ideation or domestic abuse. People in an acute state of distress would be excluded.

# 3. Co-production workshops (with lay people and pharmacy professionals)

Three co-production day workshops will then be held, with 8 lay people and 4 pharmacy staff representatives in each (total of 36 participants). The lay people will be recruited from the previous focus groups, in addition to local networks and organisations (as above).

Pharmacy staff will be recruited via the Lincolnshire Training Hub. The recruitment of pharmacies, and the staff within those pharmacies, that will be participate in the intervention delivery and feasibility stage, will be conducted in parallel to the recruitment of the pharmacy staff for the co-production workshops, to ensure that different staff are used in the co-production workshops, with no contamination into the intervention delivery. All participants will receive a £75 fee as a token of appreciation (or voucher) for participating in the co-production workshops.

In the workshops, interactive techniques will be used such as brainstorming, story-boarding, role play and principles in line with nominal group techniques to co-produce:

• A conceptual design including the name, code-word or use of symbol for discreet access

- Criteria for the pharmacy site and staff taking on the role (safe person and safe space
- A protocol for delivering the service in a pharmacy setting
- Content for an education and training resource for pharmacy staff
- A promotional strategy and marketing materials

Data will be collected on flipcharts, post-its and discussion sessions will be audio-recorded. There will be preand post- correspondence with workshop participants to review proposed materials and gather views. Data will be analysed using framework analysis, and integrated with the findings from the scoping stakeholder interviews. The qualitative software programme NVivo 11 will be used.

The collated findings will inform the final components of the intervention (protocol for delivery of the intervention in community pharmacy including criteria for the staff member and the consultation room; the triage and referral resource; education and training resource; mentoring support protocol; the name of the service as a symbol or code for discreet access, the promotional strategy).

Further development by the research team will be required for the education and training package. Learning outcomes will be developed based on the findings from the framework analysis and the method of delivery will be designed to stimulate active learning, be interactive, for example using scenarios and role play with feedback on competencies. This will support the development of the learner from "knows" through "knows how" and "shows" to "does" in accordance with Miller's Prism of Clinical Competence. A handbook for trainers and a workbook for learners will be written.

Similarly, further development of the triage and referral resource will be required by the research team, with iterative input from the local referral organisations. We have the support of the Domestic Abuse and the Suicide Prevention networks through Lincolnshire County Council.

The triage and referral tool will be a cornerstone of the study. It will consist of consultation questions, criteria and a triage grid of risk. Each level of risk on the grid will be mapped to the appropriate referral organisations. These will be agreed with the referral organisations during the co-development and will take into account their criteria for referrals and capacity. Initial work on a tool has commenced with the Crisis Team. For basic illustrative purposes only, please see the table below. The finalised grid will be accompanied by full details of clinical guidelines, contact details of referral organisations, consultation questions and protocols. A Pharmacy Operating Manual will be developed from the co-development work that contains the entire specification for the intervention including the final triage tool and signposting and referral pathways.

	Level 1 – Signs of concern	Level 2 – Active Concern	Level 3 – Immediate danger
Domestic Abuse	Uncomfortable with relationship, made to do things don't want to do. Sometimes feels frightened or threatened. +/- drug or alcohol misuse	Wanting to escape / make safety plans. Needs assistance, for example legal, housing or financial help, and/or, adverse effect on mental health, sexual or physical harm. +/- drug or alcohol misuse	psychological / sexual / physical harm, and/or suicidal as a means of escape. +/- drug or

#### Table 3: Draft indication of levels of severity assessed during triage

Suicide	Wanting change, wouldn't care if died, and/or considering death as an option to avoid something. Ambivalence about life and death. +/- drug or alcohol misuse	o	Overwhelming hopelessness, taking action to prepare for suicide, finding opportunities to be alone and avoid discovery. +/- drug or alcohol misuse
Referral Options	
 
INFORMATION – guidance and general support
 
The Samaritans
 
Women's Aid
 
Psychological interventions
 
Freedom programme
 
Consider antidepressant treatment
 
Drug & alcohol services as appropriate
 
	
 
ASSISTANCE - one to one assistance needed
 
The Samaritans
 
Women's Aid
 
Tailored psychological interventions and support with a specific person
 
GP / psychiatry
 
Drug & alcohol services as appropriate
 
Social care
 
	
 
PROTECTION – immediate intervention required
 
A&E, Specialist services, Mental Health Crisis Services, the Police
 
Drug & alcohol services as appropriate
 
Social care
 

The draft grid consists of three levels of risk: Level 1 – Signs of Concern, Level 2 – Active Concern and Level 3 – Immediate Danger. These levels are applied to the categories of: Suicidal Ideation, Suicidal Ideation with drug/alcohol misuse, Domestic Abuse, Domestic Abuse with drug/alcohol misuse. Signs and symptoms are listed for each category and level of risk, plus details of appropriate referral organisations.

Clients accessing the service will be guided through a series of questions in the consultation that will allocate them to a level and type of risk section of the triage grid. Options for onward referral or management will be discussed with the client in a shared-decision making manner and the recommendation or actual referral will be recorded. Health status questions based on an EQ5D assessment will be asked as part of the consultation. This will enable us to map EQ5D to each of the type and level of risk sections and scope the feasibility of health economic assessment measures.

Referrals will either be made directly by the member of staff, or the client will be advised to make contact with an agency if less urgent and agreed. The logistics of getting to a referral is important. In level 3 risk, help would come directly to the client. We will ensure that our resource contains details of locations, public transport and consideration of care of dependents.

Documentation and templates will be written to support appropriate record keeping and of text to be used to support any referrals made in writing (e-mail or letter). Marketing materials will be produced in-line with the promotional strategy.

Protocols will be produced for the requirements of pharmacies taking part (e.g. sound-proof consultation room), the person delivering the intervention, the process for receiving the client and directing to the consultation room, the conduct of the consultation and the record-keeping after the consultation. These protocols will form the basis of the fidelity checks at the monthly support visits.

**C. Modelling** – The entire intervention and its components will be finalised, with consideration of RE\_AIM (Reach, Effectiveness, Adoption, Implementation, Maintenance), preparation of documentation for data collection in the feasibility stage and finalisation of outcomes for feasibility study.

### Phase 2: Feasibility Randomised Control Trial

**D. Recruitment and Training –** 12 community pharmacies will be recruited to take part in the study, with 8 as interventions and 4 as controls. Purposive sampling will be used to recruit three pharmacies per category of rural/small pharmacy, rural/commercial store, uon-rural/small pharmacy, non-rural/commercial store, with a spread across different socio-economic areas (based on deprivation index from Office for National Statistics). Randomisation will then be conducted to give 2 pharmacies from each of the four categories as interventions (total of 8), and 1 pharmacy from each of the four categories as a control (total of 4).

A minimum of three members of staff from each pharmacy will be recruited in the intervention pharmacies, with one of them being a pharmacist (total of 24 staff). Recruitment will be through the Local Pharmaceutical Committee (LPC) and will involve consent from the pharmacy employer for chain pharmacies. The LPC are partners in this study and as such are very supportive and do not foresee any problems with recruiting pharmacies. Information sheets and consent forms will be provided, both for consent of the pharmacy to take part, and for staff participants. Intervention pharmacies will receive an expenses payment of £1500, and control pharmacies a payment of £500.

The participating staff will then be trained in two evening sessions, which will be interactive and involve active learning. The pharmacy sites will be visited to ensure they meet the requirements for the study, which are to have regular staff and pharmacist (not locums), and to have a consultation room that is sound-proof. Participants will be asked to complete the Continuing Professional Development (CPD) Reaction Questionnaire before and after the training. This is a validated tool for assessing the impact of CPD activities on health professionals' behaviour intentions in clinical practice. This will allow us to assess their perceived level of knowledge, skills and attitudes for delivering the intervention. Each participating member of staff will also undertake 2 mock consultations with a member of the research team to embed their learning in situ. One consultation will be on suicide prevention and one on domestic abuse.

**E. Implementation of Intervention –** The service will be promoted through a variety of settings including social media, supermarkets, pubs, community centres, sports centres, religious venues and hairdressers (depending on COVID-19 restrictions), in addition to a press release, a radio advert and the website.

The service will be implemented for 6 months (see Appendix 2 for client flow diagram). During this time the participating pharmacy staff will have monthly supervisory follow up visits from the researcher to check on fidelity of service delivery and offer support, plus access to a monthly online mentoring session with a psychotherapist to debrief on any distress that may have been incurred or any ethical issues that have been encountered.

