### **OUTCOME MEASURES/ENDPOINTS**

#### PRIMARY OUTCOME MEASURE/ENDPOINT

The primary outcome measure for this study will be the number of community pharmacy consultations for people enquiring about or seeking support for domestic violence or suicidal ideation, categorised per issue and level of severity.

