#### Quantitative data

There are three sets of quantitative data: the evaluation of pharmacy staff learning, the intervention measures and the community e-survey. To assess the impact on pharmacy staff learning (using the CPD Reaction Questionnaire), baseline and post-training data scores will be compared. For both the CPD Reaction Questionnaire and the community e-survey, categorical variables will be analysed using the chi-squared test or Fisher's exact test as appropriate. Continuous data will be analysed using the within-group t-test or Wilcoxon signed rank-test as appropriate. Statistical significance will be assessed at the 5% (two-sided) level. All statistical analyses will be conducted using IBM Statistical Package for Social Sciences (SPSS) 22.

All client and pharmacy intervention / control data will be processed using R Version 3. The demographics and characteristics of the samples will be initially summarised using frequencies and percentages for categorical variables and mean and standard deviation (if normally distributed) or median and interquartile range (if not normally distributed) for continuous variables.

The main outcome in this feasibility study is the number of community pharmacy consultations for people enquiring about or seeking support for domestic violence or suicidal ideation per issue and level of severity. Descriptive comparisons will be made between intervention and control pharmacies. Appropriate multivariable linear regression models will explore differences between intervention and control groups in means and 95% CIs. As the feasibility study is not powered to detect effectiveness, the focus will be on whether 95 % CIs include a meaningful difference. This will seek to inform a sample size calculation for a future definitive trial.

The final evaluation of feasibility will involve the integration of the qualitative and quantitative data and will include an economic evaluation. In the economic analysis, a societal perspective will be taken into consideration. Business data including staff time will be used to inform the findings. Cost per client will be estimated by dividing the costs of the response service by the total number of clients accessing the service in the intervention group. An incremental cost-effectiveness ratio (ICER) will be determined to explore the affordability and potential cost-effectiveness of the intervention and inform a future trail rather than provide a definitive comparison

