# STUDY SETTING

- One-to-one interviews will take place in a setting that is most convenient to the participant.
- Focus groups and all workshops will take place at the School of Pharmacy, University of Lincoln.
- The feasibility study will involve community pharmacies recruited from the Lincolnshire area.

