#### Phase 2: Sampling of pharmacies

A sampling framework will be used to recruit three pharmacies per the following category with a spread across different socio-economic areas (based on deprivation index from Office for National Statistics):

- Rural small pharmacy / rural large pharmacy
- Non-rural small pharmacy / Non-rural large pharmacy

Randomisation will then be conducted to give 2 pharmacies from each of the four categories as interventions (total of 8), and 1 pharmacy from each of the four categories as a control (total of 4).

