#### 3. Co-development workshops

Lay people: Members of the public will be invited from relevant patient forums, relevant charities, survivor support groups, the local Recovery College etc. via distribution of a flyer (and social media post) through a contact at those organisations. Expressions of interest will be followed up with a participation information sheet, consent form and a phone call from the researcher. In addition, participants from the lay focus groups will be invited to continue with the study and participate in a co-development workshop.

Pharmacy staff representatives: Pharmacy staff will be identified via the Lincolnshire Training Hub. To ensure that different staff are invited in the co-production workshops and intervention delivery, recruitment to both research activities will be conducted in parallel. This will ensure there is no contamination in the delivery of the intervention.

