#### b. Business data

Business data will be collected in order to evaluate whether taking on the service detracts or enhances normal pharmacy activity. Data will include prescription and service items. These data will be collected at the beginning of the study retrospectively for the 6 months prior, and during the 6 months of the implementation. All costs of the intervention will also be recorded.

In the control (comparison) pharmacies, the same business data will be collected in addition to the number of queries or interventions made for domestic abuse, and for suicidal ideation, and whether any of these were through an alternative scheme (for example "Ask for ANI"). We are including control pharmacies as this will provide useful data for a future trial and because we anticipate that the baseline levels of requests for assistance with DA will increase with public awareness of "Ask for ANI".

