33	Effectiveness of dissemination and promotion of intervention		70% of more or customer survey respondents aware of the service (intervention)	50% of more or customer survey respondents aware of the service (intervention)	30% of more or customer survey respondents aware of the service (intervention)	
34	Final consideration of the feasibility of the actual intervention. Are all the components of the intervention feasible and needed? Are there any other components that should be added?	Consideration of: 2,3,4,9,10,11,12, 14,15,16,17,18, 20,21,30,32, 33 &34 By research team, PPI panel and CTU				
35	Feasibility of a future trial – Is a trial possible?	Consideration of: 1,5,6,7,8,10,11,12, 14,15,16,17,18,19, 20,21,22,23,24,25, 26,27,28,29,30,31, 32 & 34 and questions in 35 Research team and CTU				
	What will be primary and secondary outcomes in a future cluster RCT? What are the feasible differences in primary outcome between the intervention and control groups, and the estimated intraclass correlation? Would stratification be required in the trial (type of pharmacy,					

Page 48 of 50

urban/rural location,			
socioeconomics of area,			
ethnic diversity of			
area)?			
Should sub-groups be			
considered? Is it			
feasible to randomise?			
Is it feasible to recruit			
controls?			
Power calculation and			
sample size required,			
for whole sample and			
any sub-groups.			
Possible sources of			
contamination, for			
example staff moving			
between pharmacies.			
How data would be			
analysed?			
Can quality of life,			
acceptability and			
satisfaction, and other			
health economic criteria			
be measured?			
What would be the			
requirements for future			
funding?			
	1		

 \*It is expected that should a criteria be recorded as red, this will be reviewed by the study team and adjustments made accordingly to any future design.

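### The control count is open to contamination from promotion that is not confined to intervention catchments, and the control log has no item to measure it

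*Protocol*

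**What the plan says.** **Promotion.** Under Phase 2, E. Implementation of Intervention, the service is advertised through social media and a range of public venues, "in addition to a press release, a radio advert and the website". No geographic limit is stated.

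**Location of the arms.** Study Setting says: "The feasibility study will involve community pharmacies recruited from the Lincolnshire area". Under Phase 2: Sampling of pharmacies, three pharmacies are recruited in each of four categories and two of the three are randomised to intervention, leaving "1 pharmacy from each of the four categories as a control (total of 4"). No distance or separate catchment is required between arms.

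**Outcome and its use.** "The primary outcome measure for this study will be the number of community pharmacy consultations for people enquiring about or seeking support". Under Quantitative data the arms are compared and "the focus will be on whether 95 % CIs include a meaningful difference", with the aim of informing the sample size of a definitive trial. Appendix 1, criterion 35, asks "What are the feasible differences in primary outcome between the intervention and control groups". It also lists sources of contamination among its questions, with staff moving between pharmacies as the example.

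**Control log.** Under b. Business data, controls supply a count of queries or interventions for each issue and "whether any of these were through an alternative scheme". Criterion 27 repeats this, naming Ask for ANI and safe-space requests.

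**Workshop staff.** Pharmacy staff in the co-production workshops are recruited in parallel with, and kept separate from, those delivering the service. Of this the protocol says: "This will ensure there is no contamination in the delivery of the intervention".

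**The concern.** Promotion is one of the co-developed parts of the intervention, yet radio, press and web channels have no natural boundary around eight pharmacies. Someone prompted by them could ask at a control pharmacy, and a query recognised there would enter the control count. Promotion could equally draw people who would have asked at a control pharmacy to an intervention pharmacy.

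The control arm is included to supply data for a future trial and to track an expected rise in domestic abuse requests as Ask for ANI becomes known. If study-prompted queries sit unmarked in the control count, neither the background rate nor the contamination question in criterion 35 can be answered from the data collected. An analysis plan cannot recover an item that was never recorded.

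A second, weaker route is staff. The separation rule aims to protect intervention delivery, and no exclusion criterion keeps a workshop participant from working in a control pharmacy.

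**Working it through.** The protocol gives no power, effect size or SD for the pharmacy comparison (the number of pharmacies is described as pragmatic), so there is no stated figure to reproduce. The check is whether the log can identify what is asked of it.

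**1. What the control log identifies.** Write the control total as T = B + A + S, where B is background queries, A those through other schemes, and S those prompted by this study.
- Recorded: T and A (b. Business data; criterion 27).
- Not recorded: B or S separately. Only B + S = T − A is known.
- Illustration with assumed counts: T = 12 and A = 4 leave B + S = 8. Every split from S = 0 to S = 8 fits the log. Over four controls, the background rate could be anywhere from 0/4 = 0 to 8/4 = 2 per pharmacy.

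**2. Is there a baseline to help?** The six-month retrospective collection is described for prescription and service items (b. Business data; criterion 26). Criterion 27 mentions no earlier period for queries, and the Schedule of Procedures marks control enquiries only during intervention delivery. The schedule alone is weak evidence, since it also shows business data only in that column, but the text agrees with it on enquiries.

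**3. The two arms compared.** Intervention clients who consent are asked why they chose the service, with its name and logo among the example reasons (a. Usage and referral data). Controls record nothing corresponding.

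**4. Leverage of one query under 8:4 allocation.**
- Diverted from intervention to control: the control mean rises by 1/4 and the intervention mean falls by 1/8, so the difference shrinks by 0.25 + 0.125 = 0.375.
- Newly prompted at a control: the difference shrinks by 1/4 = 0.25.
- Drawn from control to intervention: the difference widens by 0.375.

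The sign depends on which flow dominates, and the document does not say.

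**5. Consequence for a future sample size.** With SD held fixed, n is proportional to 1/difference². The distortions below are assumptions, not protocol figures.

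| Assumed distortion of the difference | 10% | 20% | 30% |
|---|---|---|---|
| Shrunk: 1/(1 − f)² | 1/0.81 = 1.23 | 1/0.64 = 1.56 | 1/0.49 = 2.04 |
| Widened: 1/(1 + f)² | 1/1.21 = 0.83 | 1/1.44 = 0.69 | 1/1.69 = 0.59 |

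The entries multiply the sample size that the undistorted difference would give. They show why it is worth measuring S. They do not estimate it.

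**The case against.** **The document shows an open route, not contamination.** Many of the listed channels are local venues, and the Study Summary places survey respondents in the locality of the intervention pharmacies. Control staff would also have to recognise and log a query made through a discreet code word or symbol. This stands: a reader might infer that promotion covers the county and does reach the controls, but the protocol says neither.

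**Ask for ANI is already handled.** A reader might infer that spillover cannot be told apart from growing Ask for ANI use. It can, because that use is recorded separately. Only the remainder is unidentified.

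**Contamination is already on the list.** Criterion 35 asks about it. That is right, but no client-level item is specified to answer it.

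**Details come later.** Promotion is a Phase 1 output, and data-collection documents are prepared at the modelling step. That leaves room to add the item, but b. Business data and criterion 27 already state what controls record, and this item is not there.

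**The staff route is thin.** Pharmacies for the feasibility stage are recruited in parallel with workshop staff and before randomisation, through a different channel, which may separate control staff in practice. Nothing shows that any workshop participant works in a control pharmacy. This largely stands: it is a gap in the wording of the rule.

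**The comparison is exploratory.** That limits the consequence, but supplying parameters for a future trial is what the comparison is for.

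**Conclusion.** The point holds as a gap in measurement. Promotion is unbounded, both arms are in one area, and the control log cannot divide the non-scheme queries into background and study-prompted. The contamination question in criterion 35 therefore cannot be answered for this route, and the background rate behind the future sample size is uncertain by an unknown amount.

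A reader might go further and conclude that the difference is biased towards zero by a calculable amount. The document does not support that. It gives no counts, no share of enquirers who would go to a control pharmacy rather than to one outside the study, and no basis for the sign. The multipliers above rest on assumed distortions and a fixed SD.

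The correction is cheap and worth making. It does not threaten the study's main feasibility aims.

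**What to change.** 1. In b. Business data and criterion 27, add one control-log item: whether the query mentioned this study's service (its name, symbol, card or promotion). Staff complete it from what the client volunteers, with no extra questioning.
2. Report control queries with and without those marked, and use the split as the measured contamination for criterion 35. Because it relies on volunteered mentions, treat it as a lower bound.
3. Record whether any control-pharmacy staff attended a co-production workshop, since the present rule aims only to protect intervention delivery.

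The cost is one log item and one staff record per control pharmacy. Control staff must also be told enough about the service to recognise a mention of it, which is itself a small exposure.

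Two stronger measures are not recommended. Requiring all promotion to name the participating sites would work against the discretion the service is designed for. Barring every pharmacy that employs a workshop participant (up to 3 × 4 = 12 staff) would shrink a sampling frame that must fill four categories of three.
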